Study Sponsor	VRHealth, [name]		
Protocol Number	VRP02		
Study Title	Evaluation of the Performance of VRP-Clinic in the Support of Rehabilitation in Healthy Subjects: A prospective, open label, single arm study design		
Projected Study Period	Initiation Date: July 2017	Completion Date: August 2017	
Study Device	VRP-Clinic		
Device Description and Indication for Use	VRP-Clinic is a software system that is coupled with virtual reality hardware and head movement sensors, aimed at gamification of physiotherapy training		
Study Objectives	
Primary objective To verify that the movements included in a VRP-Clinic VR training session are self-explanatory and recognized by clinicians
 
Secondary objectives To verify that these movements are considered useful for rehabilitation.
		
Study Design	
Single center, prospective, open label, single arm.
 
Following screening visit, eligible subjects will be enrolled into the study. Each subject will perform a series of neck movements guided by the VRP-Clinic software. The duration of the actual training session is expected to be 5 minutes.
 
Every session will be recorded by video during which the face of the subject will be covered by the VR headset.
 
The video will be evaluated by clinicians. They will identify each movement seen on the video from a predefined list and define if such a movement is recommended as part of a rehabilitation training program
		
Study Duration	Study duration from the first enrollment to completion is expected to be four months.		

Study Protocol

VRP-CLINIC SOFTWARE EVALUATION - IN SUPPORT OF REHABILITATION

Protocol#

VRP02

Version #,
Date.

Version 01
22-March-2017

Page 5 of 12

Study Population	Twenty (n=20) healthy subjects will be recruited
Main Inclusion Criteria:	
1. Healthy male or female2. Age 18-65
Main Exclusion Criteria:	
1. History of neck related disorders (Whiplash, disc degeneration disease or other acute cervical spine conditions)2. Current neck pain3. Under medical treatment or observation for any health-related issue during the study4. Recent trauma5. Oncology background6. Acute disease/illness7. Pregnancy.8. Using drugs that could potentially affect physical function and balance (such as corticosteroids, antipsychotics or antidepressants)9. Vision problems that require glasses (not all frame types can fit into the headset)
Study Endpoints	
Primary Endpoint: Number of VRP-Clinic neck movements that the evaluator recognizes as useful for rehabilitation. Success acceptance criteria defined as: 80%
 
Secondary Endpoint: Safety – Record of any adverse event occurring during the study. All AEs will be recorded and evaluated as part of the risk management for the device

	Study Protocol			
	VRP-CLINIC SOFTWARE EVALUATION - IN SUPPORT OF REHABILITATION			
Protocol#	VRP02	Version #, Date.	Version 01 22-March-2017	Page 6 of 12

INTRODUCTION

One of the most common musculoskeletal dysfunctions in the population is dysfunction of the cervical spine reaching an annual prevalence of 30-50% in western societies and associated with considerable pain, disability, and costs [1, 2].

Physical therapies are first line treatments aimed at improving muscle strength and range of motion, often requiring considerable commitment by subjects over a long period of time [3] and frequently requiring a home exercise program for a successful outcome [4]. However, compliance to home exercises is not as high as desired therefore, it is imperative to include new motivational interventions to increase compliance.

Virtual reality (VR) technology has been used for several decades for a variety of psychosocial interventions. The use of VR was studied for a variety of rehabilitation conditions [5, 6]. Specifically, the effect of neck exercises using VR was previously tested on both asymptomatic individuals and patients with chronic neck pain and was shown to be useful in increasing cervical motion [7-9].

STUDY RATIONAL

In recent years, commercial and research groups have been studying the effect of VR systems on the rehabilitative progress and developing new platforms. As the variety of available products widens, each system focuses on specific hardware and different rehabilitation aspects. The software presented in the current study focuses on the rehabilitation of the upper body.

STUDY OBJECTIVES

The current study was designed to evaluate neck movements performed according to the VRP-Clinic software, and to verify that they promote physical activities that correspond with physical rehabilitation.

STUDY DEVICE

Indications for Use

VRHealth's VRP-Clinic software, coupled with compatible VR (virtual reality) hardware (headset and supporting PC) is intended to promote physical rehabilitative processes of individuals requiring training of their head and neck muscles/joints as part of a physical therapy session.

Prior to the first session using VRP-clinic, a medical practitioner will assess the patient and will determine the selection of movements included in such training.

Device Description

VRP-clinic Software

VRP-Clinic software is used with several supported hardware platforms, delivering the same experience in each. Currently, the VRP-Clinic software supports Oculus rift and HTC VIVE

 
המרכז הרפואי שערי צדק ירושלים
	Study Protocol			
	VRP-CLINIC SOFTWARE EVALUATION - IN SUPPORT OF REHABILITATION			
Protocol#	VRP02	Version #, Date.	Version 01 22-March-2017	Page 7 of 12

platforms – both systems use a PC based virtual reality platform and infra-red sensors to detect head movement of the user.

A description of the software algorithm, a major routine/function level flow chart, a signed validation document, and a risk analysis table can be found in the Investigator Brochure.

Hardware platform

VRP-Clinic software is used with several supported hardware platforms, delivering the same experience in each. Currently, the VRP-Clinic software supports Oculus rift and HTC VIVE platforms – both systems uses a PC based virtual reality platforms and used infra-red sensors to detect head movement of the user. In the current study, the Oculus rift platform will be used. A description of the Oculus rift device and the manufacturer details can be found in Investigator Brochure.

STUDY DESIGN

Overview

Single center, prospective, open label, single arm.

The study will take place at Shaare Zedek Medical Center (SZMC). The study will include a single visit. Twenty (n=20) healthy subjects will be recruited to this study. Subjects must meet the eligibility criteria detailed in the protocol and sign the informed consent form prior to any study procedure.

Each subject will receive an explanation from the study team on the device and study procedures. Medical and demographic information will be collected.

The subject will put on the VR headset and perform a series of neck movements guided by graphic instructions appearing in the VR environment. The study team will record any adverse event (AE) if such happens during/post training.

The session will be recorded with a video camera. Camera recording will start after the VR headset is placed on the subjects' head and terminate before removing it, to ensure the participants' privacy.

The video will be viewed and evaluated separately by 4 clinicians. The clinicians will identify each movement seen on the video from a predefined list and determine if such a movement is recommended as part of a rehabilitation training program for neck related pathologies.

Endpoints:

Primary Endpoint

Number of VRP-Clinic neck movements that the assessing clinician recognizes as rehabilitation movements.

Success acceptance criteria defined as: 80%

Secondary Endpoint:

Safety – Record of any adverse event occurring during the study.

All AE's will be recorded and evaluated as part of the risk management for the device

Study Duration

	Study Protocol			
	VRP-CLINIC SOFTWARE EVALUATION - IN SUPPORT OF REHABILITATION			
Protocol#	VRP02	Version #, Date.	Version 01 22-March-2017	Page 8 of 12

Duration of subject's participation: 30 minutes of which the actual exercise is expected to take not more than 5 minutes

Study duration: The total study duration from recruitment to final data collection is estimated to be four months

STUDY POPULATION AND SUBJECT SELECTION

Source and sample size

Twenty (n=20) healthy adult subjects will be included in this study. The subject will be recruited by the investigator by use of an IRB approved advertisement.

Eligibility

Each subject will be evaluated by the Investigator to assess his/ her suitability for entry into this study according to the following criteria:

Inclusion Criteria

Eligible subjects must meet all of the following inclusion criteria:

1. Healthy male or female
2. Age 18-65

Exclusion Criteria

Eligible subjects must not meet any of the following exclusion criteria:

1. History of neck related disorders (Whiplash, disc degeneration disease or other acute cervical spine conditions)
2. Current neck pain
3. Under medical treatment or observation for any health-related issue during the study
4. Recent trauma
5. Oncology background
6. Acute disease/illness
7. Pregnancy.
8. Using drugs that could potentially affect physical function and balance (such as corticosteroids, antipsychotics or antidepressants)
9. Vision problems that require glasses (not all frame types can fit into the headset)

The investigator may withdraw a subject if, in his clinical judgment, it is in the best interest of the subject or if the subject cannot comply with the protocol. At the discretion of the investigator, these subjects may be replaced. Attempt should be made to complete any examinations.

Subject Termination

In case of dropout or subject removal the investigator will describe the reason for discontinuing the subject's participation in the Termination CRF.

Compensation

At the end of the session, subjects will receive a coupon for use at the local cafeteria for purchase of a hot drink and cake ("café u maafe") approximately worth 15 NIS as compensation for their time.

	Study Protocol			
	VRP-CLINIC SOFTWARE EVALUATION - IN SUPPORT OF REHABILITATION			
Protocol#	VRP02	Version #, Date.	Version 01 22-March-2017	Page 9 of 12

STUDY PROCEDURES

Screening

Eligibility: the volunteer will be screened to determine if he/she meets the study inclusion/exclusion criteria.

Informed consent Prior to the study visit, informed consent will be obtained. When the participant fully understands the procedure, possible benefits and risks of the study, the subject will be asked to sign and date the informed consent document.

Subject number If the subject meets the study inclusion/exclusion criteria, the subject will be assigned the next consecutive number.

Medical history and demographic information: Basic medical and demographic information will be collected including age, gender, height, weight, head circumference, general medical background and specific information related to head/neck.

Interventions and procedures:

Subject Preparation and Instructions

The subject will sit on a steady chair, with back support, in front of a desk where the device sensors are located. Once starting the training program, the subject will receive instructions appearing in the graphic VR environment:

Neck movements

The software will guide the subjects to perform neck movements.

EVALUATIONS

Physiotherapist Evaluation and Assessment of Videos

1. Identification of each movement seen in the video from the list detailed in "Neck Movement" section
2. Determining if the use of such movement is recommended for rehabilitation

Safety

All adverse events (AEs) will be documented and evaluated as part of the risk management for the device

	Study Protocol			
	VRP-CLINIC SOFTWARE EVALUATION - IN SUPPORT OF REHABILITATION			
Protocol#	VRP02	Version #, Date.	Version 01 22-March-2017	Page 10 of 12

STATISTICAL CONSIDERATIONS AND ANALYSIS

Sample Size Justification

The rationale for the sample size is based on obtaining exact 95% confidence intervals for the activity movements which achieved 80% success. When the sample size is 20, a one-sided 95.0% confidence interval for a single proportion using the large sample normal approximation will extend at most 0.18 from the observed proportion.

Subject Accountability

A CONSORT flow diagram will be presented that will include the number of subjects screened and reasons for screening failures; the number of subjects, who were enrolled, as well as the reasons for all enrollment discontinuations grouped by major reason; A list of discontinued subjects, protocol deviations, and subjects excluded from the analyses.

Data Analysis

Descriptive statistics and summary tables will be provided giving sample size, absolute and relative frequency of categorical variables and sample size, arithmetic mean, standard deviation, median, minimum and maximum, percentiles and 95% CI (Confidence Interval) for means of continuous variables. All measured variables and derived parameters will be listed individually and, if appropriate, tabulated by descriptive statistics.

Study Hypothesis – Primary Endpoint:

The number and percentage of neck movements which achieve a success rate of at least 80% will be tabulated. Exact 95% binomial confidence intervals will be calculated for the rate of neck movements which achieve 80% success.

Safety - Secondary Endpoint

Adverse events will be coded according to coding dictionaries (MedDRA version 13.1 or higher) and presented in tables by system organ class, preferred term. The number and percentage of subjects who experienced any adverse events will be tabulated.

ADVERSE EVENTS

In this study, Serious Adverse Experience (SAE) is to be reported by the investigator within 24h to the IRB. The “Adverse Experience” CRF should be filled in all events of SAE and in other cases of Adverse Experience (AE) which, in the judgment of the investigator, affect this protocol.

Anticipated Side Effects

In this study, we are not anticipating any side effects.

Anticipated Adverse Effects/Risks

The movements not expected to cause any pain or discomfort.

	Study Protocol			
	VRP-CLINIC SOFTWARE EVALUATION - IN SUPPORT OF REHABILITATION			
Protocol#	VRP02	Version #, Date.	Version 01 22-March-2017	Page 11 of 12

MISCELLANEOUS

Ethical Considerations

Prior to study initiation the site shall obtain an Institutional Review Board (IRB)/Helsinki approval of the study. Any changes in the study protocol, informed consent forms, or investigator must be re-approved by the IRB and the approval documented. All subjects enrolled in the study will provide their consent prior to entering the study. An informed consent form shall be signed by the subject. The investigator will retain the forms as part of the study records.

This study will be performed in accordance with the Declaration of Helsinki, in agreement with the guidelines for conducting a clinical investigation in accordance with the principles of ICH GCP outlined in the E6 document and IRB guidelines. By signing the present protocol, participants in the study commit themselves to carry it out in accordance with local legal requirements

Protocol Amendments

Possible with IRB approval.

Study Monitoring

Study monitoring visits include a pre-study site evaluation and site initiation visit, periodic monitoring visits during the course of the investigation, and a final termination visit at the conclusion of the study. The frequency of the monitoring visits will vary depending on the subject enrollment rate, the quantity and quality of data collection.

Study Documentation

Study documents include protocol and MOH documents, approvals, insurance, signed ICFs, copy of CRFs, training materials, SAE reports, investigator site file

Case Report Forms (CRFs)

Case Report Forms will be established to collect the required demographic and clinical information, as described by this protocol and the variables to be analyzed. Case Report Forms will be completed by the investigator or a designee who will be properly trained on study procedures and data recording requirements. The investigator will maintain a separate enrollment log with the corresponding subject name, initials and subject code. All CRFs will have 1 original clearly filled with a ball point pen. Any changes, amendments or additions to the forms will have to be marked though with a single line, dated, and initialed. The investigators will maintain a copy of the CRFs.

Study Termination

If the Principal Investigator determines that the conditions do not allow the continuation of the study, then it will be terminated. Among the conditions that may justify the study termination without limitation are the followings:

- Subject safety
- Inability to enroll subjects at acceptable rate

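### No step asks subjects about symptoms, the post-training AE window has no end, and the AE form rule conflicts with recording every AE, so mild events may be missed and 0/20 would be weak evidence

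*Combined protocol and SAP*

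**What the plan says.** - **Endpoint.** The synopsis and the Endpoints section give one secondary endpoint: "Safety – Record of any adverse event occurring during the study". Both add that every AE will be recorded and used in risk management for the device.
- **Collection.** Study Design, Overview: "The study team will record any adverse event (AE) if such happens during/post training". The same section says "The study will include a single visit". Study Duration gives each subject's participation as "30 minutes of which the actual exercise is expected to take not more than 5 minutes".
- **Evaluation.** Evaluations, Safety, says only: "All adverse events (AEs) will be documented and evaluated as part of the risk management for the device". It gives no question, checklist, time point or closing date.
- **Form.** The Adverse Events section requires the AE case report form for all serious events and for "other cases of Adverse Experience (AE) which, in the judgment of the investigator, affect this protocol".
- **Analysis.** Safety - Secondary Endpoint, in the statistical section, tabulates the number and percentage of subjects with any AE.
- **Expectation.** No side effects are anticipated, and under Anticipated Adverse Effects/Risks: "The movements not expected to cause any pain or discomfort".

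**The concern.** Mild neck discomfort or unsteadiness is something the subject feels and staff may not see. If nobody is required to ask, a subject who says nothing is counted as free of AEs. Nor does the video help after training, because recording stops before the headset comes off. The protocol takes a head and neck history beforehand but has no matching question afterwards.

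Even an event that staff learn of can drop out. Under the form rule, a non-serious AE that the investigator does not think affects the protocol needs no AE form, although the planned table counts subjects with any AE.

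What is at stake is how a low or zero count is read. The protocol already expects no side effects, pain or discomfort. A count of zero obtained without asking would seem to confirm that expectation without having tested it, and it would then feed the device's risk management.

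**Working it through.** **The plan's own figure.** The plan computes nothing for safety. Its only computed figure is the 0.18 in Sample Size Justification, which concerns movement recognition. It reproduces: 1.645 × √(0.5 × 0.5 / 20) = 0.184, which rounds to 0.18. It has no bearing on AE capture.

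**The texts side by side.**

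1. *Window.* The endpoint covers the study; the collection instruction covers during and after training. No section says when the post-training period ends, and no contact after the visit is described. The two windows are not shown to be the same.
2. *Elicitation.* Overview, Interventions and procedures, and Evaluations contain no step in which the subject is asked about symptoms.
3. *Form.* The synopsis, Endpoints and Evaluations call for every AE. The Adverse Events section requires the form for a subset. The Case Report Forms section makes those forms the route for the variables to be analysed, and the protocol names no other source for the any-AE table. These statements cannot all be followed as written.

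**What 0/20 would mean.** Inputs: n = 20 (from the protocol); true share of subjects with an AE, p (assumption, 5% to 30%); share of those subjects whose AE is captured, s (assumption, 25% to 100%, taken as equal for all). The documents give neither p nor s.

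Chance that the table shows no AE: P(0 of 20) = (1 − p·s)^20.

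| Assumed p | s = 1 | s = 0.5 | s = 0.25 |
|---|---|---|---|
| 5% | 0.95^20 = 36% | 0.975^20 = 60% | 0.9875^20 = 78% |
| 10% | 0.90^20 = 12% | 0.95^20 = 36% | 0.975^20 = 60% |
| 20% | 0.80^20 = 1% | 0.90^20 = 12% | 0.95^20 = 36% |
| 30% | 0.70^20 = 0.1% | 0.85^20 = 4% | 0.925^20 = 21% |

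At p = 10%, the expected number of subjects with a recorded AE is 20 × 0.10 × s: 2.0, 1.0 and 0.5 for the three columns.

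Exact one-sided 95% upper limit after 0/20: 1 − 0.05^(1/20) = 13.9%. That limit applies to the recorded rate p·s. The limit on p is 13.9%/s:

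- s = 1: 13.9%
- s = 0.75: 18.5%
- s = 0.5: 27.8%
- s = 0.25: 55.6%

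**The case against.** The strongest case on the other side is that the protocol promises to record every AE, that saying an AE is recorded if it happens is ordinary wording and filters nothing, and that staff are free to ask. The case report forms and the risk analysis in the Investigator Brochure are not among the documents and may contain a prompt. Safety is descriptive with no acceptance threshold, the primary endpoint is untouched, and exposure is at most about 5 minutes of seated neck movement in healthy adults.

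Much of this stands, and it rules out several stronger readings that a reader might infer:

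- *That the endpoint is certain to under-count.* The documents give no symptom rate and no capture rate, and the assumed range includes full capture.
- *That the protocol prescribes passive recording.* It leaves the method unstated, which is a different defect.
- *That the window closes when the subject leaves.* The text sets no end, and it does not confine the post-training period to the visit or say how much of the 30 minutes remains after training.
- *That the exclusions for current neck pain and for drugs affecting balance show the sponsor expected mild or delayed symptoms.* Those items may simply define a healthy sample. The second concerns a drug effect, not a device effect, and no exclusion mentions mild or later symptoms.

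None of this supplies the missing question or the missing end of the window. Nor does it remove the conflict over the form. A promise to document all AEs states an aim; it does not say how a symptom that only the subject can feel comes to light.

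**Conclusion.** The point holds as a gap in method together with a contradiction in the text. The protocol sets no way of eliciting AEs and no end to their collection, and its form rule is narrower than both its recording commitment and its planned table. Mild subjective events may be missed. That they will be missed is not shown.

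The size cannot be derived from the documents. If capture is complete, 0/20 excludes true rates above 13.9% (one-sided 95%); if only half of affected subjects are captured, it excludes only those above 27.8%. Without a stated method, a reader of the results cannot tell which applies. The symptom and capture rates are illustrations only; the conflict over the form rests on no assumption.

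This should be corrected, but it does not threaten the primary result. Its effect is confined to a descriptive endpoint after a short exposure, and to the use of those data in risk management.

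**What to change.** 1. In Study Design, Overview, and Evaluations, Safety: after headset removal and before the subject leaves, ask every subject one open question plus a few fixed yes/no items (for example neck pain, discomfort, unsteadiness), and record all answers, including the negative ones.
2. State when AE collection starts and ends. If it ends at departure, label the endpoint as AEs during the visit. A brief later contact is an option if a longer window is wanted, but the point does not depend on it.
3. Reconcile the form rule in the Adverse Events section with the synopsis, Endpoints and Evaluations, so that every AE recorded reaches the any-AE table. Without this step, a symptom reported in answer to the new question could still go without an AE form.

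The cost is about one minute per subject, or about 20 minutes over 20 subjects, and a few lines on a form. No extra subjects or staff are needed. The downside is that the AE count may look less favourable than one obtained without asking.

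### Ratings cover only movements seen on the video and are not compared with the movement instructed, so the 80% result can be biased upward and does not test whether the instructions are self-explanatory

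*Combined protocol and SAP*

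**What the plan says.** The synopsis states the primary objective as: "To verify that the movements included in a VRP-Clinic VR training session are self-explanatory and recognized by clinicians". The usefulness of the movements for rehabilitation is the secondary objective.

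The instruction comes from the software. Study Design, Overview: "The subject will put on the VR headset and perform a series of neck movements guided by graphic instructions appearing in the VR environment". Study Procedures, Neck movements: "The software will guide the subjects to perform neck movements".

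The rating starts from the film. Study Design, Overview: "The clinicians will identify each movement seen on the video from a predefined list and determine if such a movement is recommended". Evaluations repeats the rule, with "Identification of each movement seen in the video from the list detailed in" the neck movement section as step 1 and the recommendation as step 2. Four clinicians rate separately.

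The primary endpoint in the synopsis is: "Number of VRP-Clinic neck movements that the evaluator recognizes as useful for rehabilitation". The body of the protocol has a similar endpoint, and both set success at 80%. The analysis under Study Hypothesis – Primary Endpoint is: "The number and percentage of neck movements which achieve a success rate of at least 80% will be tabulated".

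The visible text does not define success for a single movement or state its denominator. It also does not say how to score a movement that was omitted, performed differently from the instruction, or identified as another one.

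**The concern.** Whether an instruction explains itself is a question about the link between what the software asked for and what the subject did. Testing it requires a comparison of the two, and the plan describes none.

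The two failures that would show an unclear instruction are therefore not required to lower the result. A subject who does not perform the movement leaves nothing on film to rate. A subject who performs a different listed movement leaves something that a clinician can identify, recommend and count.

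This is a single-arm study judged against a fixed 80% criterion, so no comparator would reveal the inflation. A pass would show that the filmed movements look like rehabilitation exercises. It would not show that the software elicited the movements it intended.

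**Working it through.** **1. The plan's own figure.** Sample Size Justification gives 0.18 as the largest distance of a one-sided 95% limit from the observed proportion at n = 20. With the normal approximation at p = 0.5, 1.645 × √(0.5 × 0.5 / 20) = 0.1839, so the figure reproduces. It concerns precision only. Its one bearing here is that it treats 20 as the number of observations behind the proportion.

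**2. Objective against measurement.**
- Objective: movements self-explanatory and recognised. This needs instructed against performed, and performed against identified.
- Rating: identify what is seen, then say whether it is recommended.
- Endpoint: a count of movements judged useful or rehabilitative, with no condition that the movement is the one instructed.
- Analysis: movements reaching 80%, with no stated denominator.

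The step from instructed to performed appears in the objective and nowhere in the measurement.

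**3. Omission, one movement and one rater.** The documents give no omission or recognition rates, so these are assumptions. Let r be the proportion of performed movements that are recognised and k the number of the 20 subjects who perform the movement. With only seen movements in the denominator, the expected rate is r whatever k is. Over all instructed subjects it is r × k/20. With r = 0.95:
- k = 19: 0.95 × 19/20 = 90.25%
- k = 18: 0.95 × 18/20 = 85.5%
- k = 17: 0.95 × 17/20 = 80.75%
- k = 16: 0.95 × 16/20 = 76%

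The verdict at r = 0.95 changes between 3 and 4 non-performers, that is, at 20% omission in whole subjects. In general the tipping point is 1 − 0.80/r: 20% at r = 1, 15.8% at 0.95, 11.1% at 0.90 and 5.9% at 0.85.

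**4. Chance that a movement reaches 80%.** Take r = 0.95, omission probability o and wrong-movement probability w. Seen-only: M ~ Bin(20, 1 − o), S given M ~ Bin(M, 0.95), pass if S/M ≥ 0.80; a wrong movement is credited like a right one. Matched over all 20: S ~ Bin(20, 0.95 × (1 − o − w)), pass if S ≥ 16.

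| o | w | Seen-only | Matched over 20 |
|---|---|---|---|
| 0 | 0 | 0.997 | 0.997 |
| 0.10 | 0 | 0.990 | 0.847 |
| 0.10 | 0.10 | 0.990 | 0.456 |
| 0.20 | 0.10 | 0.988 | 0.148 |

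If the plan is read as seen-only, it is nearly insensitive to failed guidance. If guidance never fails, the two rules agree.

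**5. Substitution.** A fixed denominator of 20 per movement deals with omission but not fully with substitution. A subject told to do A then B who does B then A shows both movements. Both are identified and recommended, and both count, although neither instruction was followed at the time.

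**The case against.** A reader might infer that the plan prescribes a seen-only denominator and that upward bias is therefore demonstrated. The documents do not support that. No denominator is written, and the sample size statement at n = 20 allows a fixed one. On that reading, a movement performed and recognised in 12 of 20 subjects scores 60% and fails, as it should. Likewise, with a fixed denominator per movement, a subject who does B when told A normally costs A a success. Substitution inflates the result only under a pooled or seen-only count, or where movements are exchanged as in step 5. What stands is that the plan as written permits these counts and rules none of them out.

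A reader might also infer that the raters could not check the instruction because only the subject is filmed. The protocol says when recording starts and stops, but not what is in the frame.

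The list of neck movements is not visible in the text available, and the case report forms and Investigator Brochure were not available. The list may be the software's own set of movements. That would link the set to the software, but not an individual rating to an individual instruction.

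Finally, these are healthy adults who receive an explanation beforehand, and no document suggests omission near 20%. Failures may be rare, and the change would then hardly move the result. But rare failure is what the primary objective sets out to show, so it cannot be assumed. The listing of deviations and discontinued subjects may document gross non-performance, but it does not put those movements back into the success rate.

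**Conclusion.** The point holds as a gap between the primary objective and what is scored. A plan followed to the letter could count a substituted listed movement as a success and need not count an omitted one as a failure. The 80% result can therefore be biased upward, and it does not test whether the instructions are self-explanatory.

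The direction is conditional on how the unstated denominator is applied, and the size is unknown. At an assumed 95% recognition of performed movements, up to 3 non-performers in 20 leave the verdict unchanged (80.75%) and 4 reverse it (76%). With lower recognition the tipping point comes earlier. All performance and recognition rates here are assumptions, taken for one movement and one rater.

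**What to change.** In Study Design (Overview and Endpoints), Evaluations, and the primary endpoint analysis:

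- Make the unit each movement the software instructed, for every subject who started the session, including any later withdrawn or replaced.
- Have the clinicians identify the movements while masked to the programmed sequence.
- Score recognition as a success only if the identification matches the instructed movement. Count omitted, unidentifiable and mismatched movements as failures, over all instructed movements.
- Report the rating of whether a movement is recommended separately, for the secondary objective.
- State how the four clinicians' ratings combine into the success rate, which the visible text leaves open.

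Settle this before rating begins, because an omitted movement leaves no rating to recover afterwards.

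The cost is protocol and case report form wording, plus matching each video to the programmed sequence. No session log or time stamp is described, so the sponsor should confirm that the sequence can be retrieved. No extra subjects or raters are needed. The downsides are that the reported success rate may be lower and that a rater's misidentification counts against the movement.
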